10.4.3.6.4 Plasmid DNA Lymphoma Vaccine, Stanford University

Excised neoplastic peripheral lymph node(s) of 12 adult patients with B-cell lymphomas were used to create patient-specific DNA plasmids expressing each patient's tumor-specific variable region of a chimeric immunoglobulin molecule. ^{Timmerman2002} These were administered as vaccines to the patients after completion of chemotherapy in three series of vaccinations, each with three monthly doses. The first series used IM needle injections in escalating dose amounts of antigen. Beginning 17 months later for the second series, and 14 months thereafter for the third series, the highest dose in series 1 (1800 µg) was administered by Biojector system, of which 80% was by IM cartridge (0.8 mL in one posterior upper arm) and 20% in two adjacent ID-spacer injections of 0.1 mL in the opposite arm. In series 3, GM-CSF plasmids were also injected. The researchers carefully observed local and systemic reactions for one hour, and patients used a diary card to record subsequent reactions.

After vaccination series 2, 9 of 12 patients demonstrated immune responses, either humoral (6), T cell (6) or both (3). After series 3, 7 of the 9 responders to series 2 continued to display the measured immune responses, and there was one new responder.

The incidence and severity of both the series 2 Biojector IM injections were indistinguishable from that experienced after the needle-syringe IM injections of series 1. Similarly, the series 3 injections were indistinguishable from the series 2 for local reactions. The authors wrote, "No appreciable local reactions were observed at the sites of ID inoculation" and "No systemic toxicity was noted".

10.4.3.6.5 Colorectal Cancer Vaccine, Oxford Biomedica, UK

In a trial among patients with colorectal cancer (Duke's stage D), the Biojector system with intradermal spacer was used for six patients receiving three doses ($1x10^8$ pfu in 0.1 mL at 0, 4, and 8 weeks) of a modified vaccinia Ankara (MVA) vector expressing tumor-associated antigen 5T4 (TroVax[®]), and compared with 16 patients receiving the same antigen intramuscularly by needle-syringe in dose escalation ($5x10^7$ to $5x10^8$ pfu).^{Harrop2003, HarropMs, Reinis2004} If clinical or immunological response was detected, two more doses at 14 and 20 weeks were offered.

Most patients showed proliferative responses to the protein or peptide 5T4 antigen, although responses tended to be greater and less transient in the IM than ID groups. The most commonly reported treatment-related adverse events were non serious, local ones relating to the injection site. There was a

HIRRC/CDC Needle-free Intradermal	Page 67	File: 4785-ID-INF-Prot-Engl-2008Jun24.doc
Influenza Study - CDC-ISO-4785	of 138	2008-Jun-24

notably higher incidence of injection site erythema in the intradermal injection group (3 of 6, 50%).

10.4.3.6.6 Adult Volunteers, HIV vaccine, Karolinska Institute

At the Karolinska Institute in Stockholm, Sweden in February, 2005, the first human volunteers began receiving vaccination in an ongoing HIV vaccine trial using a multigene DNA vaccine (animal studies described earlier in section 10.4.3.5.8).^{Brave2005}

10.4.4 Method of Assigning Participants to Treatment Groups

For each phase of the study (I and II), an independent, outside party (e.g., a member of the Data and Safety Monitoring Board - DSMB) will determine in advance the injection method to be used for each participant identification (ID) number to be assigned in the study:

• IM-NS-0.25 (control)	(intramuscular, needle-syringe, full dose)
• IM-NS-0.1	(intramuscular, needle-syringe, reduced dose)
• ID-JI-0.1	(intradermal, jet injector, reduced dose)

The outside party shall provide copies of these treatment group assignments for each study ID number to at least two [other] members of the DSMB. These records shall remain confidentially in their custody in separate locations outside of the Dominican Republic and released only at the time and in the manner as described in this protocol.

A study nurse will assign permanent participant ID numbers consecutively to each patient in the chronological order in which the corresponding informed consent form is signed and he or she is enrolled.

10.4.4.1 Equal Allocation by Sextuplet Blocks

Treatment group assignments will be made by generating a series of "sextuplet" blocks of 6. For each block, the independent party will assign in random order two injections from each of the three study arms to a randomly selected position $(1^{st}, 2^{nd}, 3^{rd}, 4^{th}, 5^{th}, \text{ or } 6^{th})$ within the block. Thus, there will be 36 (3! x 3!) possible orders for any given block of six, as illustrated in Table 4.

		Sequence Position					
		1st	2nd	3rd	4th	5th	6th
	A.	IM-NS-0.25	IM-NS-0.25	IM-NS-0.1	IM-NS-0.1	ID-JI-0.1	ID-JI-0.1
Sample	B.	IM-NS-0.25	IM-NS-0.1	IM-NS-0.25	IM-NS-0.1	ID-JI-0.1	ID-JI-0.1
	C.	ID-JI-0.1	IM-NS-0.1	IM-NS-0.1	ID-JI-0.1	IM-NS-0.25	IM-NS-0.25
Blocks	D.	IM-NS-0.1	IM-NS-0.25	IM-NS-0.25	ID-JI-0.1	ID-JI-0.1	IM-NS-0.1
	etc.						

Table 4. Examples of random sextuplet blocks for allocating samples

HIRRC/CDC Needle-free Intradermal	Page 68	File: 4785-ID-INF-Prot-Engl-2008Jun24.doc
Influenza Study - CDC-ISO-4785	of 138	2008-Jun-24

For combined phases I and II, a total of 80 blocks will be prepared (480 assignments), 30 more than the target sample size (n=450), in case of dropouts or other contingency. This system will provide for equal or nearly equal sizes of each study group throughout the enrollment process.

10.4.4.2 Avoiding Block Counting

To prevent "block counting" to predict the route of vaccination for a child, the first block will be split randomly into two parts (1+5, 2+4, 3+3, 4+2, or 5+1), with its first segment applicable to the initial participant ID numbers, and its remainder applied to the final ID numbers.

For example, if block 1 were randomly determined to follow sample sequence A in Table 4 above, and is then randomly split into "1 + 5", then participants would be assigned their injection route as follows:

Last 3 digits are
Participant ID no.* \downarrow
CDC-ISO-4785-001
CDC-ISO-4785- 002 – 475
CDC-ISO-4785- 476
CDC-ISO-4785- 477
CDC-ISO-4785- 478
CDC-ISO-4785- 479
CDC-ISO-4785- 480

Vaccination Group

IM-NS-0.25 (as per block 1, example A) (in accordance with blocks 2 through 79) IM-NS-0.25 (as per block 1, example A) IM-NS-0.1 (as per block 1, example A) IM-NS-0.1 (as per block 1, example A) ID-JI-0.1 (as per block 1, example A) ID-JI-0.1 (as per block 1, example A)

Similarly, if block 1 were randomized to follow sequence D in Table 4 above, and is randomly split 4+2, then participants would be vaccinated as follows:

Participant ID no.* \downarrow	Vaccination Group
CDC-ISO-4785-001	IM-NS-0.1 (as per block 1, example D)
CDC-ISO-4785- 002	IM-NS-0.25 (as per block 1, example D)
CDC-ISO-4785- 003	IM-NS-0.25 (as per block 1, example D)
CDC-ISO-4785- 004	ID-JI-0.1 (as per block 1, example D)
CDC-ISO-4785- 005 – 478	(in accordance with blocks 2 through 79)
CDC-ISO-4785- 479	ID-JI-0.1 (as per block 1, example D)
CDC-ISO-4785- 480	IM-NS-0.1 (as per block 1, example D)

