responses suggesting protection against influenza can safely be induced in young children by two reduced doses one month apart of 0.1 mL of a trivalent inactivated influenza vaccine				
(INF) administered by the intradermal (ID) route with an investigational ID spacer on a U.S				
doses by needle-syringe (N-S	licensed needle-free jet injector (JI), compared to two standard intramuscular (IM) 0.25 mL doses by needle-syringe (N-S) in this age group. The locale is a developing country where			
financial restraints for the use of full-dose influenza vaccine would limit protection from				
influenza pandemic threat, where N-Ss pose dangers and drawbacks in clinical use, and				
influenza pandenne uneat, where in-5s pose dangers and drawbacks in chinical use, and				

HIRRC/CDC Needle-free Intradermal	Page 4
Influenza Study - CDC-ISO-4785	of 138

where Mantoux-type N-S ID injections are difficult to administer during mass campaigns.

Objectives (§9.6):

The **primary endpoint** of this study is to measure the percentage of participants recruited at age >6 -to- <24-months with seroconversion on hemagglutination inhibition (HI) assay of serum collected at least one month after two doses of influenza vaccine (INF) administered in a reduced-dose volume of 0.1 mL intradermally (ID) by needle-free jet injector and intramuscularly (IM) by conventional needle-syringe (N-S), compared to standard IM injection of full 0.25 mL doses.

Secondary objectives of this study are to determine for the above comparison seroprotection rates, geometric mean titers, and the extent and frequencies of local and systemic reactions.

Methods (§10):

Randomized, observer-blinded, clinical pilot (phase I) trial of safety, followed by a clinical (phase II) trial of safety and non-inferiority of immune response to the standard route and dose for the merged participants from both phases.

Phase I - Influenza-vaccine naïve children (n=48) aged ≥ 6 -to- <24 months will be randomized in a 1:1:1 ratio to the following three study arms, each to receive two doses on days 0 and 28 of trivalent inactivated influenza (INF) vaccine (Vaxigrip®, Sanofi Pasteur, Lyon, France) into the left thigh (<12 months) or left deltoid (≥12 months):

- Group "ID-JI-0.1" (n=16) reduced 0.1 mL INF doses administered intradermally (ID) by needle-free jet injector (JI) (Biojector[®] 2000 subcutaneous syringe no. 2 (green color code), with 2cm investigational spacer, Bioject Medical Technologies, Inc., Portland, OR, USA)

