10.1.2 Phases

The studies will be conducted in two phases:

Phase I. 48 children assigned randomly into 3 study arms of 16 each.

Phase II. Upon analysis of adverse events and clearance by the DSMB, an additional 402 infants of the same age range will similarly be enrolled into the same three study arms of 134 participants each.

Total participants in phase I and II = 450 (150 in each of three study arms).

If phase II is not pursued for whatever reason, sera from phase I will be assayed as described below, after which the study group codes will be unblinded for analysis of phase I by the investigators.

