10.10 Criteria for Proceeding to Phase II

Upon unblinded analysis by the DSMB (see section 10.11) of the results of the phase I study, the observed adverse reactions will be tallied by the DSMB for each of the study arms (control IM-NS-0.25, investigational IM-NS-0.1 and ID-JI-0.1). Either or both investigational study arm(s) for which an observed numbers of reactions exceeds the number observed in the IM-NS-0.25 control arm by the following degree for any reactions listed will be eliminated from the phase II study. If both investigational arms are thus eliminated, the study will not proceed to phase II.

	Excess = no. in investigational arm less no. in control arm
Serious Adverse Reaction, possibly- or probably-related	≥3
Fever >40° C, possibly- or probably-related	≥4
Injection site whole-limb swelling	≥4

HIRRC/CDC Needle-free Intradermal	Page 103	File: 4785-ID-INF-Prot-Engl-2008Jun24.doc
Influenza Study - CDC-ISO-4785	of 138	2008-Jun-24

Injection site induration >5 cm in diameter	≥5
Injection site erythema >5 cm in diameter	≥5
Injection site pain level 3 (cries upon moving limb)	≥5

For example, if four (4) children in the IM-NS-0.25 control arm experience inducation of >5 cm, eight (8) do so from the IM-NS-0.1 arm, and nine (9) from the ID-JI-0.1 arm, then the IM-NS-0.1 study arm may proceed to phase II, but the ID-JI-0.1 arm will be dropped from phase II.

Based upon this analysis and any other relevant information, the DSMB will decide whether or not the study should proceed to phase II as designed, should be modified and then proceed, or should be terminated. This decision shall be duly informed to the investigators, without revealing unblinded information nor study-group-specific analyses. Regardless of a DSMB decision permitting phase II, the study sponsor may elect for any reason not to proceed, and to terminate the study after phase I.

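### The single 480-number list ends phase I in mid-block, so the stated 16 children per arm arises in only about 27% of lists; the effect on the raw-count phase II gate is modest

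*Protocol*

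**What the plan says.** The Synopsis (Methods) has the 48 phase I children "randomized in a 1:1:1 ratio to the following three study arms", with n=16 for each. Section 10.1.2 repeats it: "48 children assigned randomly into 3 study arms of 16 each".

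On how the numbers are produced, the protocol says two things:

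- Section 10.4.4 opens "For each phase of the study (I and II), an independent, outside party" and has that party fix the injection method for each ID number in advance. This can be read as one list per phase.
- Section 10.4.4.1 describes one list: "For combined phases I and II, a total of 80 blocks will be prepared (480 assignments"). This leaves a reserve of 30 beyond the 450 planned. Each block of six is to "assign in random order two injections from each of the three study arms".
- Section 10.4.4.2 cuts block 1 at random into k and 6−k places, with k from 1 to 5, and keeps the two parts apart, "with its first segment applicable to the initial participant ID numbers, and its remainder applied to the final ID numbers". Both worked examples put the remainder at the IDs that end with 480.
- Section 10.8.3 confirms that the split is between the first and last enrollees of the study, not of a phase.

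Section 10.4.4 assigns IDs consecutively, so phase I is IDs 001 to 048. Section 10.10 then decides whether an investigational arm continues by "Excess = no. in investigational arm less no. in control arm", with thresholds of 3, 4 or 5 children and no denominator.

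**The concern.** Forty-eight is exactly eight blocks of six, so unsplit blocks would give 16 per arm with certainty. Splitting block 1 across the whole study shifts every later block boundary by the length of the first segment. The cut at ID 048 then always falls inside a block. The numbers that would restore balance sit at the end of the 480 list, beyond the 450 children planned, and would normally never be used.

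Two things follow. The stated phase I arm size is not what the described list delivers in most cases. And the 10.10 gate, which subtracts numbers of children and not proportions, compares like with like only when the arms are equal. If they differ, an investigational arm can meet or miss a fixed excess partly because it holds more or fewer children than the control arm.

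**Working it through.** **Inputs.** Phase I size 48 and 16 per arm (10.1.2); blocks of six with two places per arm (10.4.4.1); split k + (6−k) with k = 1 to 5 (10.4.4.2); consecutive IDs (10.4.4). The protocol says the split is random but gives no probabilities; I assume the five are equally likely.

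The protocol states "Thus, there will be 36 (3! x 3!) possible orders for any given block of six". The number of distinct orders is 6!/(2!·2!·2!) = 90. Row A of the protocol's Table 4 puts the same arm in adjacent places from the first position, so its own examples are not limited to two successive permuted triplets, which is what 3! × 3! would count. I use 90 equally likely orders.

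**Stated figure.** 48/3 = 16, and 8 whole blocks × 2 = 16. It reproduces as the target.

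**List as described.** IDs 001–048 hold k places of block 1, then 48 − k = 42 + (6 − k) further places: seven whole blocks (14 per arm) and the first 6−k places of another. The remainder (48 − k) mod 6 is 5, 4, 3, 2, 1 for k = 1 to 5. It is never 0.

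The arms are 16/16/16 only if the k places left off the last block have the same arm composition as the k places taken from block 1. The chance of that is the sum of squared composition probabilities:

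- k = 1 or 5: 3 × (1/3)² = 1/3 = 33.3%
- k = 2 or 4: 3 × (1/15)² + 3 × (4/15)² = 51/225 = 17/75 = 22.7%
- k = 3: (2/5)² + 6 × (1/10)² = 11/50 = 22.0%

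Average: (1/3 + 17/75 + 11/50 + 17/75 + 1/3)/5 = 67/250 = **26.8%**. A simulation of 100,000 lists also gave 26.8%.

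| Phase I arm sizes, any order | Share of lists |
|---|---|
| 16/16/16 | 26.8% |
| 17/16/15 | 64.3% |
| 18/15/15 | 3.3% |
| 17/17/14 | 3.3% |
| 18/16/14 | 2.3% |

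All arms lie within 15–17 in 26.8 + 64.3 = 91.1%. A given investigational arm equals control in size in 29.0% of lists, differs by at most one child in 71.9%, and by two or more in 28.1%. The case of 18 investigational v 14 control occurs in 2.27%/6 = 0.38% for a given arm.

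**Effect on the 10.10 gate.** X and Y are independent binomials with the realised arm sizes; the quantity is P(X − Y ≥ threshold). The 20%, 30% and 35% v 10% rates are assumptions, as the protocol gives none for this purpose.

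| True rates, threshold | 16 v 16 | 17 v 15 | 15 v 17 | Average over lists |
|---|---|---|---|---|
| 20% both, ≥5 | 2.3% | 3.4% | 1.4% | 2.3% |
| 30% both, ≥5 | 4.0% | 6.6% | 2.3% | 4.2% |
| 35% v 10%, ≥5 | 41% | 49% | 33% | 41% |

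For scale, section 10.4.2.6 reports severe-reaction frequencies for this vaccine at 6 to 36 months of 2.1% (fever), 0.3% (pain), 0.3% (induration) and 0% (erythema). At 2.1%, an excess of 4 or more has probability 0.02% at 16 v 16 and 0.04% at 18 v 14. At 0.3%, an excess of 5 or more is of the order of one in a billion at either.

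**The case against.** The strongest reply concerns consequence, not combinatorics. Section 10.4.4.1 promises only equal or nearly equal groups, and 15 to 17 per arm in 91% of lists is nearly equal; the 16 can be read as a planned size. Averaged over lists, the gate behaves almost exactly as with equal arms. The 10.10 events are extreme, and the nearest rates in the protocol are so low that a difference of a child or two in arm size hardly matters. The DSMB is unblinded, holds the allocation list and so knows the denominators. Section 10.10 also lets it weigh other relevant information.

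Most of this stands and sets the weight of the point. It does not remove the conflict. The sections still describe a list that misses the stated 16 about three times in four, section 10.4.4 still points to a list per phase, and the numerical rule in 10.10 is worded as elimination without reference to arm size. The DSMB applies it once, to one list, so the average over lists does not describe that single decision.

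Two stronger readings go further than the protocol allows. A reader might infer that the gate is materially unreliable, for instance from the 10.1% false excess at 18 v 14 with a 30% rate. That needs a list arising in 0.38% of cases and an assumed rate far above the severe-reaction rates in 10.4.2.6. A reader might also infer that, once an arm is dropped, the sealed phase II envelopes would still assign children to it. The protocol does not say when phase II envelopes are prepared, section 10.4.4 speaks of each phase, and 10.10 allows modification before phase II. That is an ambiguity, not a demonstrated error.

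**Conclusion.** The concern holds as a minor inconsistency. As sections 10.4.4.1, 10.4.4.2 and 10.8.3 are written, phase I cannot end on a block boundary, and the stated 16 per arm is reached in about 27% of lists. The 22% to 33% range covers any weighting of the five splits. The usual departure is one child either way.

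The overall operating characteristics of the 10.10 gate are almost unchanged. In a particular realised list, a two-child difference can move the chance of a false excess up or down by about half at rates of 20% to 30%. That result depends on assumed event rates and on independence between children, and it fades to nothing at the low rates the protocol cites. The unequal sizes do not show that the gate would fail.

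**What to change.** Reconcile sections 10.4.4, 10.4.4.1, 10.4.4.2 and 10.8.3 as follows:

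- Give phase I its own list of exactly eight blocks (48 places). If the split first block is kept against block counting, put its remainder at the end of the phase I numbers. The arms are then 16/16/16 as assigned, with certainty.
- Have the independent party generate the phase II list separately after the 10.10 decision, for the arms that continue, and say when its envelopes are prepared. The 402 places are 67 blocks of six if all three arms continue, plus reserve.
- Leave the 10.10 thresholds as they are. They are a safety criterion, and the numbering can be corrected without touching them.
- In the same edit, correct the count of block orders from 36 to 90, and the block range in the first worked example: IDs 002–475 are 474 numbers, or 79 blocks, so blocks 2 through 80 and not 2 through 79.

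The cost is two lists in place of one, with the phase II envelopes made later. No extra children, visits or procedures are needed. Equal assignment does not guarantee equal evaluable numbers after dropout.

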10.4.4.3 Allocation Group Randomization Cards

The study investigators shall provide the outside, independent party with sufficient numbers of *allocation group randomization cards*, samples of which are pictured in **Figure 16** through **Figure 19** below.

HIRRC/CDC Needle-free Intradermal	Page 69	File: 4785-ID-INF-Prot-Engl-2008Jun24.doc
Influenza Study - CDC-ISO-4785	of 138	2008-Jun-24

The text of the mock injection card to avoid the extravaccination of a 3rd "insurance" dose on day 56 (**Figure 19**, section) translates as follows in English:

Do NOT administer vaccine to this child. Apply a bandage even though there is no injection
 Keep the child in the injection room por the time it usually takes to give an injection. Do not inform the parents or doctors that no injection was given. Revealing this "mock injection" can compromised the blinding of the study. Destroy this card before inviting the parents to enter or yourself leaving the room. Apply a bandage in the place where an injection would be given: in the left thigh for children <12 months of age. In the left deltoid for children 12 months and older.

Figure 16. Randomization card for "IM-NS-0.25" group.

HIRRC/CDC Needle-free Intradermal	Page 70	File: 4785-ID-INF-Prot-Engl-2008Jun24.doc
Influenza Study - CDC-ISO-4785	of 138	2008-Jun-24

Figure 17. Randomization card for "IM-NS-0.1" group.

Figure 18. Randomization card for "ID-JI-0.1" group.

HIRRC/CDC Needle-free Intradermal	Page 71	File: 4785-ID-INF-Prot-Engl-2008Jun24.doc
Influenza Study - CDC-ISO-4785	of 138	2008-Jun-24

Figure 19. Card for mock 3rd "insurance" injection for group "IM-NS-0.25".

The outside, independent party who randomly determined the treatment group assignments, as described above, shall insert the cards in accordance with the randomization results into corresponding participant-ID-numbered *allocation group randomization envelopes* (see below). A peel-off "confirmation sticker" with the participant's study ID number and dose (1 = "A", 2 = "B", 3 = "C") will be affixed to the face of each card for attachment to the CRF to verify accuracy in administering the correct type of injection.

10.4.4.4 Allocation Group Randomization Envelopes

The outside, independent party shall prepare four (quadruplicate) sets of *allocation* group randomization envelopes. The envelopes shall be sealed, opaque, and not permit visualization of its contents upon holding up to the light. For each set, consecutive participant ID numbers shall be written, printed, or stickered clearly on the outside of each envelope, e.g., "CDC-ISO-4785 – **001**", "CDC-ISO-4785 – **002**", etc.

Three sets of envelopes, the GREEN, YELLOW and RED sets shall be provided to the Dominican Principal Investigator for use in the study injection room for the FIRST, SECOND, and THIRD study injections, respectively. They shall be marked on their covers "1 - Primera", "2 - Segunda", and "3 - Tercera",

HIRRC/CDC Needle-free Intradermal	Page 72	File: 4785-ID-INF-Prot-Engl-2008Jun24.doc
Influenza Study - CDC-ISO-4785	of 138	2008-Jun-24

respectively. (Envelopes for the RED set for the "insurance" dose will contain the IM full-dose randomization card shown in **Figure 16** for the two reduced-dose groups IM-NS-0.1 and ID-JI-0.1. RED envelopes for the full-dose group, IM-NS-0.25, having already received the standard 2-dose regimen, will contain a card indicating a mock injection, as shown in **Figure 19**.).

A fourth set of envelopes, the BLUE set, similarly identified on their outside by the participant's study ID number, shall be kept sealed in a secure location (e.g., locked safe) in the custody of the director of the HIRRC. The individual BLUE envelope for a specific participant shall be opened only upon the application of the Dominican Principal or Senior Investigators in the event of a serious adverse reaction for which treatment will depend upon knowledge of the vaccination method (IM-NS-0.25, IM-NS-0.1, or ID-JI-0.1) received by that participant.

The *allocation group randomization envelope* shall be opened by the unblinded injection nurse only when she and the other unblinded study staff (holding assistant) are all in the injection room with the participant of corresponding ID number, and his or her parents have left the room temporarily.

After preparing the proper injection equipment with the proper dose of vaccine, the two staff shall confirm that the delivery device is the same as indicated on the card, its peel-off "confirmation sticker" shall be affixed to the designated box on the corresponding vaccination page in the CRF (parts 7, 11, or 15), and then the card shall be destroyed and disposed in a locked trash receptacle in the same cubicle. After the vaccination, the device used to administer it shall be removed from view and the participant parent invited into the cubicle to sit down and console the child.

